4.3. TIME PERIOD OF THE STUDY

Table 2 Start and finish dates

Task	Start Date	End Date
Management/advisory structures	04/2021	07/2021
Staff Recruited (Research Manager)	06/2021	07/2021
Functional specifications and care plan template	04/2021	12/2021
Development of cost and consumer outcomes questionnaires (and database)	04/2021	12/2021
Ethics approval	04/2021	07/2021
Trial commencement/Recruitment	03/2022	12/2022
Trial completion	04/2023	06/2023
Evaluation reporting	01/2023 ⁴	04/2024
Translation/dissemination	05/2024	06/2024

4.4. ENDPOINTS

PRIMARY ENDPOINTS

Differences between the intervention and comparison groups in changes in the frequency and quality of preventive care from their reported usual shared care to 3-months:

1. Increased % of consumers for whom each health risk is measured and recorded over the preceding 3 months*
2. Increased % consumers who have been vaccinated against influenza over the preceding 3 months
3. Decreased % consumers with high CVD risk who have not received a prescription for either an anti-hypertensive or lipid lowering drug.
4. Increased % consumers who report advice/referral for smoking cessation, diet education and physical activity over the preceding 3 months.

* Health risks are itemised in Table 3.

SECONDARY ENDPOINTS

Differences between the intervention and comparison groups in changes from their reported usual shared care to 3-months:

5. Increased % MHS consumers have a care plan (GPMP and TCA) in last 3 months
6. Increased consumer rating of extent to which providers (MH & GP) are working to a common care plan in the past 3 months
7. Improved quality of communication between MHSs and GPs in last 3 months
8. Reduced number of ED attendances and hospitalisations in last 3 months
9. Increased number of visits to GP in last 3 months
10. Improved consumer experience of providers (MH & GP) working to a common (shared) care plan in the past 3 months (qualitative analysis)
11. Increased scores on Domain 1 (Feeling understood and supported by healthcare providers) and Domain 7 (Navigating the healthcare system) of the Health Literacy Questionnaire
12. Increased score on Patient Activation Measure (PAM-13)
13. Improved diet and physical activity behaviours
14. Reduced Absolute Cardiovascular Disease Risk score **
15. Reduced diabetes risk score using AUSDRISK ***
16. Improved levels of most recently recorded results from health risk screening*
17. Reduced costs of hospitalisations in last 3 months
18. Reduced out of pocket costs of participants
19. Improvements in Quality of Life as assessed by the EQ5D-5L.

* Health risks are itemised in Table 3.

** Information needed for CVD risk score is provided in Table 4

*** Information needed for AUSDRISK score is provided in Table 5.

Table 3 Health risks

Health risks	Units/options	Normal range/goals
Systolic & diastolic blood pressure (BP)	mmHg	<130/85 mm Hg
Weight and height (height 'ever recorded') - for body mass index (BMI)	Weight: kg Height: cm BMI: Weight/Height*Height	reduced BMI for those above healthy weight
Lipids: - total cholesterol (TC), - Low-density lipoprotein (LDL), - High-density lipoprotein (HDL), - triglycerides (TG)	mmol/L	TC <5.5 mmol/L HDL > 1.0mmol/L
Fasting blood glucose (FBG)	mmol/L	3.0 - 6.0 mmol/L
Glycated haemoglobin (HbA1c)	mmol/mol	15-42 mmol/mol
smoking status	Y/N	N
alcohol consumption	number of drinks each week	Max 10 drinks per week
waist circumference	cm	<94 cm men < 80cm women
Kidney function test: - Estimated Glomerular Filtration Rate (eGFR) - microalbuminuria	eGFR - GFR number microalbumin: mg	eGFR <60 mL/min/1.73 m2? Less than 30 mg is microalbumin

Table 4 Information needed for CVD risk score

Elements	Units/options
Gender	M/F
Age	years
Systolic blood pressure	mmHg
Smoking status	Y/N
Total cholesterol	mmol/L
HDL cholesterol	mmol/L
Diabetes	Y/N
ECG shows left ventricular hypertrophy (LVH)	Y/N/unknown

Table 5 Information needed for AUSDRISK score

Elements	Units/options
Age	Years
Gender	M/F
Country of birth	Australia/ Asia, Middle East, North Africa, Sth Europe / Other
Aboriginal, Torres Strait Islander, Pacific Islander or Maori descent	Y/N
Family history of diabetes	Y/N
Past high glucose	Y/N
Hypertension treatment (medication for high blood pressure)	Y/N
Smoking status	Y/N
Fruit and veg every day	Y/N
Physical activity 2.5 hours per week	Y/N
Waist circumference	cm

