4.5. SITES

Site Name/s	The study site is Sydney LHD. Teams involved in the study will be four adult Community Mental Health 'Core' Teams at Canterbury, Croydon, Camperdown and Marrickville
Site Contact/Investigator	[name]
PHO	YES
If a non-PHO is an EEA in place?	N.A.
Study Procedures	
Procedures have been developed in consultation with site team leaders and staff and will be the consistent across all four mental health teams. The number of active consumers with each team varies from 278 to 448. It is anticipated that each team will recruit approximately one-quarter of the total sample, with larger teams recruiting slightly more than smaller sites.
 
Care coordinators at each team will identify and approach potential study participants. They will be given written information to give to the consumer. With the consumer’s permission, care coordinators will provide the research team with contact details of consumers who are interested in participating in the study.
 
A research officer will contact these potential participants to explain the study, answer any questions, and obtain informed consent. In intervention sites, participant consumers will be asked to approach their GP to be part of the project or consent to the research team doing so on their behalf to recruit GPs to the study.
 
For consumers in the intervention group, if GPs provide consent to participate in the study, they and their patient are enrolled in the study and an appointment is made to install the shared care software in the practice’s computer and arrangements will be made to train the GP in its use.
 
Consumers in the comparison group will receive usual care. If their GP decline to be involved in the study, these consumers will remain enrolled in the study for intention-to-treat analysis.
 
Consumer participants will participate in a baseline survey which is repeated 3 months after their usual shared care appointment, or 3 months after 30 June for those consumers who did not attend their shared care appointment. These interviews will be conducted via telephone, online or face-to-face, depending upon the preference of each consumer.
 
All consumers will be invited to participate in a qualitative interview after the 3-month survey.
 
Care Coordinators and GPs will also be interviewed after the intervention period.

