7. OUTCOMES AND DATA SOURCES

Table 9 Outcomes and their data sources

Concept	Primary Outcomes	Data source
1 Preventive care	GP-recorded screening of health risks 6-month period post-intervention* (May-October 2023) compared with the 6-month periods: 
 • Pre-intervention (November 2022-April 2023) • In the previous year (May-October 2022) 
*"intervention" = shard care plan in Inca (May-June 2023)
	GP records
	GP-recorded prescription of antihypertensive or lipid lower medications 6-month period post-intervention* (May-October 2023) compared with the 6-month periods: 
 • Pre-intervention (November 2022-April 2023) • In the previous year (May-October 2022) 
*"intervention" = shard care plan in Inca (May-June 2023)
	GP records & HealtheNet
	Consumer-reported advice/referral from GP for smoking cessation, diet and physical activity in last 6 months	Consumer survey

Concept	Secondary Outcomes	Data source
1 Preventive care	GP-recorded care plans: GPNP and Team Care, mental health 6-month period post-intervention* (May-October 2023) compared with the 6-month periods: 
 • Pre-intervention (November 2022-April 2023) • In the previous year (May-October 2022) 
*"intervention" = shard care plan in Inca (May-June 2023)
	GP records
2 Integration of care	Consumer assessment of extent to which providers (MH & GP) are working to a common care plan in last 6 months	Consumer survey
	Provider reported quality of communication between MHSs and GPs in last 6 months	Provider survey and qualitative interviews

Concept	Secondary Outcomes	Data source
3 Health service use	ED use and hospitalisations for primary care preventable conditions and other conditions 6-month period post-intervention* (May-October 2023) compared with the 6-month periods: 
 • Pre-intervention (November 2022-April 2023) • In the previous year (May-October 2022, to check for seasonal effect) 
*"intervention" = shard care plan in Inca (May-June 2023)
	SLHD eMR (Appendix 14), Integrated Care Outcomes Database (ICOD)

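### Section 4.4 and Table 9 give two conflicting sets of primary endpoints, and the advice/referral outcome has a 6-month recall at a survey held 3 months after the appointment

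*Protocol*

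**What the plan says.** Section 4.4 defines the primary endpoints as between-group differences in "changes in the frequency and quality of preventive care from their reported usual shared care to 3-months". Four endpoints follow:

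- Recording of risks, taken singly, is the first: "Increased % of consumers for whom each health risk is measured and recorded over the preceding 3 months".
- The second is uptake of the influenza vaccine, with a 3-month look-back.
- Untreated cardiovascular risk is the third: "Decreased % consumers with high CVD risk who have not received a prescription for either an anti-hypertensive or lipid lowering drug".
- The last is the share reporting that they were advised or referred on smoking, diet or exercise, again with a 3-month look-back.

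Three of these state a 3-month look-back. The third has none of its own and takes the 3-month frame from the lead-in.

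Table 9 in section 7 lists three primary outcomes:

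- The first is "GP-recorded screening of health risks 6-month period post-intervention* (May-October 2023) compared with the 6-month periods". The two comparison periods run from November 2022 to April 2023, just before the intervention, and from May to October 2022, one year earlier.
- The second is GP-recorded prescribing of antihypertensive or lipid-lowering drugs, over the same calendar windows.
- The third is "Consumer-reported advice/referral from GP for smoking cessation, diet and physical activity in last 6 months", taken from the consumer survey. Table 10 in section 9.2 repeats its 6-month window.

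On survey timing, section 4.5 says: "Consumer participants will participate in a baseline survey which is repeated 3 months after their usual shared care appointment". Consumers with no appointment are surveyed 3 months after 30 June 2023. Table 9 and section 8.2 date the intervention (a shared care plan in Inca) to May–June 2023.

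The hypotheses (section 2), the research questions (section 3) and the main between-group comparison in 8.2 use 3 months. The administrative data in 8.2 use 6-month windows.

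**The concern.** Both lists are operative text, so this is not a difference between a change log and the current protocol. They differ in the number of endpoints, the length and anchoring of the window, and the population counted. A result on one list does not answer the question posed by the other. Untreated consumers among those at high cardiovascular risk, for example, is a different quantity from any recorded prescription among all consumers. While both lists stand, a reader cannot tell which result is the primary one.

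The second problem is narrower. A 6-month recall asked 3 months after an appointment reaches 3 months behind it. Advice given in that earlier period cannot be due to a plan that did not yet exist, yet it counts as outcome in both arms and pulls them together.

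**Working it through.** **The two lists side by side**

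| Item | Section 4.4 | Table 9 |
|---|---|---|
| Number of primaries | 4 | 3 |
| Window | 3 months, from the consumer's own shared care | 6 months; calendar-fixed for the two record outcomes, survey recall for advice |
| Influenza vaccination | primary | absent |
| Prescribing | untreated, among those at high CVD risk | any recorded prescription, no risk denominator |
| Advice/referral | 3 months | 6 months |

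**The plan's own sample size.** Inputs from sections 4.2 and 8.1: 30% vs 50%, alpha 0.05, power 0.80. Taking alpha as two-sided and using unpooled variance:

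n = (1.96 + 0.84)² × (0.3×0.7 + 0.5×0.5) / 0.20² = 90.3, rounded up to 91 per group.

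This matches the stated figure. Doubling for the design effect gives 182 per group and 364 in total, against the stated 180 and 360. The arithmetic is sound, but the protocol does not say over what window 30% and 50% are meant. The calculation stands beside a 3-month follow-up in 4.2 and a 9-month follow-up in 8.1.

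**How much of the recall is pre-intervention.** The survey is at appointment + 3 months and the recall starts at survey − 6 months, which is appointment − 3 months. With plan and appointment both in May–June 2023 and the plan no later than the appointment:

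| Plan | Appointment | Survey | Recall starts | Pre-intervention days |
|---|---|---|---|---|
| 1 May | 1 May | 1 Aug | 1 Feb | 89 of 181 (49%) |
| 30 June | 30 June | 30 Sept | 30 March | 92 of 184 (50%) |
| 1 May | 30 June | 30 Sept | 30 March | 32 of 184 (17%) |

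The third row is possible because Table 7 lets the mental health service create the plan before the first GP visit. A 3-month recall would start on the appointment date and include no time before it.

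**Illustration of the effect on power.** Assumptions: a constant monthly chance of advice, and an effective size per group of 180/2 = 90 (the planned number) or 200/2 = 100 (the 400 expected to remain). With a pooled variance under the null:

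power = Φ{[d − 1.96√(2p̄(1−p̄)/n)] / √([p₁(1−p₁) + p₂(1−p₂)]/n)}

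For 30% vs 50% this gives 79% (n = 90) and 83% (n = 100).

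*Rates read as 6-month rates, with k pre-intervention months.* The intervention-arm rate is 1 − 0.7^(k/6) × 0.5^((6−k)/6).

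| k | Contrast | Power, n = 90 | Power, n = 100 |
|---|---|---|---|
| 1 | 30% vs 47.1% | 66% | 70% |
| 2 | 30% vs 44.1% | 50% | 54% |
| 3 | 30% vs 40.8% | 33% | 36% |

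*Rates read as 3-month rates, with 3 pre-intervention months.* Comparison arm 1 − 0.7×0.7 = 51%, intervention arm 1 − 0.7×0.5 = 65%. Power is 48% (n = 90) or 52% (n = 100).

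**The case against.** The best defence is that the intended version can be traced. The version 11 entry in the version control box, dated 18 October 2023, moves the GP audit/HealtheNet data to 6-month windows and removes GP-recorded influenza vaccination. It also removes the absolute cardiovascular risk score from that audit, which may explain the lost denominator. Table 9 agrees with the entry, so 4.4 looks like text left behind. This stands as an explanation, but it does not make the two sections agree, and the entry says nothing about the survey recall.

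It is also fair that the recall problem touches only one of the three Table 9 primaries, and that the question wording is in Appendix 3, which is not shown. The 6-month label in Tables 9 and 10 is what can be judged here.

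Some stronger readings are tempting but not supported:

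- *That the endpoint set was chosen after the results were seen.* The change was logged before the May–October 2023 record window closed, and nothing shows that data drove it.
- *That power is 29%.* Halving the standardised effect gives Φ(2.80/2 − 1.96) ≈ 29%, but this is one near-worst case. It takes the planning rates as 6-month rates and the overlap as exactly half.
- *That control rates for each window can be derived from the 512 of 736 consumers with a verified health check (section 1.1).* No period is stated for that count, and the check is not a primary endpoint.
- *That separate tests of every Table 3 risk inflate the type I error by a calculable amount.* Multiplicity handling may sit in a statistical analysis plan that is not shown. The items are also likely to be correlated, so a calculation assuming independence would overstate the risk.

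**Conclusion.** The conflict between 4.4 and Table 9 is established from the text alone and needs no assumption. The protocol has four primary endpoints over 3 months in one place and three over 6 months in another, differing also on vaccination and on the prescribing denominator.

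The recall mismatch also holds, for the advice/referral outcome only. Between about 17% and about 50% of the recall is pre-intervention when plan and appointment both fall in May–June 2023. A longer gap from plan to appointment would shrink the overlap. The resulting power of 33–36%, 48–52% or 50–70% is illustrative. It depends on the constant monthly chance of advice and on which window the planning rates describe. The finding does not rest on these figures.

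**What to change.** Replace the primary list in 4.4 with one that agrees with Table 9, giving each endpoint one stated window and one denominator. Remove the primary endpoints that Table 9 no longer measures. Carry the list through sections 2, 3, 7 and 8.2, and state which window the 30% vs 50% refers to.

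For advice/referral, change the window in Tables 9 and 10 to 3 months. It should match the interval from the appointment to the survey, or from 30 June 2023 for consumers with no appointment. Apply it in both arms and with a comparable baseline window.

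May–June appointments put the follow-up surveys in August–September 2023, so they may already have been collected. If they used 6-month wording, rewording cannot repair them. In that case declare the pre-intervention overlap and make the advice outcome secondary.

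The cost is a protocol amendment and possibly the loss of primary status for the advice outcome.

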4.2. EXPECTED PARTICIPANT NUMBERS

We aim to recruit 500 consumers and expect 400 to remain in the study at 3-month follow-up (20% loss to follow up). Power calculation: Assuming 20% change in the frequency and quality of primary and preventative care received by participants, a sample size of 91 per group is required to detect a change from 30 to 50% in primary outcomes based on $\alpha = 0.05$, $1-\beta = 0.8$. Assuming a design effect due to clustering of 2, a total sample of 360 is required (180 in each group).

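### Primary endpoint 4 takes smoking-cessation advice as a percentage of all consumers rather than of smokers, and does not say how the three kinds of advice combine

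*Protocol*

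**What the plan says.** Primary endpoint 4 in section 4.4 reads "Increased % consumers who report advice/referral for smoking cessation, diet education and physical activity over the preceding 3 months". Endpoint 3 in the same list does limit its denominator to people at risk: "Decreased % consumers with high CVD risk who have not received a prescription for either an anti-hypertensive or lipid lowering drug". All primary endpoints share the lead-in "Differences between the intervention and comparison groups in changes in the frequency and quality of preventive care from their reported usual shared care to 3-months".

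The matching row of Table 9 in section 7 reads "Consumer-reported advice/referral from GP for smoking cessation, diet and physical activity in last 6 months". It names no denominator and adds no restriction to smokers. Its recall window also differs from section 4.4, which is a separate matter. The consumer-survey list in Table 10 (section 9.2) adds no restriction either.

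The inclusion criteria in section 5.1 do not require smoking, poor diet or inactivity. Smoking status is an AUSDRISK element (Table 5), and AUSDRISK is part of the consumer survey (Table 10), which is given at baseline and at follow-up.

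On sample size, section 4.2 states that "a sample size of 91 per group is required to detect a change from 30 to 50% in primary outcomes", followed by "Assuming a design effect due to clustering of 2, a total sample of 360 is required (180 in each group".

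**The concern.** Cessation advice applies to people who smoke. Over all consumers, the best attainable percentage on a smoking item is roughly the smoking prevalence, and any improvement among smokers is scaled down by that prevalence. The trial was sized on a 20-point change in its primary outcomes, so a scaled-down change is underpowered. It is also hard to interpret: a low figure could mean poor care or few smokers.

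The way the three kinds of advice are joined adds a second ambiguity:

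- **Three separate percentages:** the smoking item is diluted as described.
- **Any one of the three:** a non-smoker can qualify through diet or activity advice, and the dilution is smaller.
- **All three together:** a non-smoker can hardly ever be counted as a success.

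These are three different primary endpoints, and the text does not choose between them.

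**Working it through.** **1. Reproduce the plan's figure.** Inputs from section 4.2: 30% and 50%, alpha 0.05 (taken as two-sided; the sidedness is not stated), power 0.80. With unpooled variance,

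n = (1.960 + 0.842)² × (0.30×0.70 + 0.50×0.50) / 0.20² = 7.849 × 0.46 / 0.04 = 90.3, so 91 per group.

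This matches. A design effect of 2 gives 182 per group, against the stated 180. The effective size used below is 180 / 2 = 90 per group.

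**2. Planned power on that basis.** With p̄ the mean of the two rates and Δ their difference,

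Power = Φ{[Δ − 1.96·√(2p̄(1−p̄)/n)] / √[(p₁(1−p₁) + p₂(1−p₂))/n]}.

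For 30% against 50% and n = 90: (0.20 − 1.96×0.0730) / 0.0715 = 0.795, power 79%.

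**3. Dilution of a separate smoking item.** Assumptions, none of them given in the protocol: smoking prevalence s; the 30% to 50% change holds among smokers; no non-smoker reports cessation advice. Over all consumers the rates become 0.30s and 0.50s, with 90 effective per group. Among smokers only they stay at 30% and 50%, with 90s effective per group.

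Worked example, s = 50%:
- All consumers, 15% against 25%, n = 90: (0.10 − 1.96×0.0596) / 0.0592 = −0.285, power 39%.
- Smokers only, 30% against 50%, n = 45: (0.20 − 1.96×0.1033) / 0.1011 = −0.024, power 49%.

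| Assumed s | All consumers | Difference | Power, all | Power, smokers only |
|---|---|---|---|---|
| 30% | 9% to 15% | 6 points | 23% | 32% |
| 40% | 12% to 20% | 8 points | 31% | 41% |
| 50% | 15% to 25% | 10 points | 39% | 49% |
| 60% | 18% to 30% | 12 points | 47% | 57% |
| 70% | 21% to 35% | 14 points | 55% | 63% |
| 80% | 24% to 40% | 16 points | 64% | 69% |

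The smokers-only denominator does better in every row, and 80% is reached in none. To keep 80% power over all consumers with design effect 2, the total would be 1,304, 992 or 780 at s = 40%, 50% or 60%, against the 360 planned. The design effect is held at 2 for smokers; smaller numbers per team would, if anything, lower it.

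**4. Smoking imbalance between arms, no true effect.** Take a 10-point gap in smoking prevalence.
- Follow-up levels compared, 40% of smokers advised in both arms: 0.10 × 0.40 = 4 points of false difference.
- Difference in changes, advice rate among smokers stable: 0 points.
- Difference in changes, advice among smokers rising from 30% to 50% in both arms: 0.10 × (0.50 − 0.30) = 2 points.

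**The case against.** **The planning change was never assigned to smokers.** Section 4.2 speaks of the primary outcomes among participants, and the dilution figures move the 30% to 50% change to smokers. This is fair, and the figures are conditional on it. The denominator problem does not depend on it: a non-smoker still counts as a failure on a cessation item.

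**Scoring may be settled elsewhere.** Appendix 3 and any statistical analysis plan were not available, so a skip rule or a not-applicable answer for non-smokers cannot be ruled out. That is a reason to make the wording agree, but the protocol does state a denominator for this endpoint, and endpoint 3 shows that it writes an at-risk one where it wants one.

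**A reader might infer that a smoking imbalance between the two pairs of teams would pass directly for an effect.** The document does not support this in general. The stated contrast is a difference in changes, in which a stable imbalance cancels. Section 8.2 also adjusts for variables that differ significantly at baseline. What remains is narrower. Section 8.2 can be read as comparing outcomes after the intervention; advice rates may shift in both arms; a significance screen can miss a real imbalance; and section 5.4 does not name smoking among the confounders. With four teams randomised, an imbalance is plausible.

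**A reader might also want at-risk denominators for diet and activity advice.** The AUSDRISK items on fruit and vegetables and on weekly activity score diabetes risk; they do not define who needs advice. Table 3 also sets goals for BMI, lipids, glucose and waist, so a consumer who eats well may still warrant diet advice. All consumers is a defensible denominator for those two items.

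**The gain is modest.** This stands: about 9 to 10 points of power at 40% to 60% prevalence, still well below 80%.

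**Conclusion.** The point holds for the smoking part of endpoint 4 and for the undefined combination of the three kinds of advice. Treated as a separate item over all consumers, a 20-point change among smokers shrinks to 8, 10 or 12 points at an assumed prevalence of 40%, 50% or 60%. Nominal power falls from the planned 79% to 31%, 39% or 47%; restricting to smokers gives 41%, 49% or 57%. These figures rest on the assumed prevalence, on placing the planned change among smokers, and on a simple two-proportion comparison with design effect 2. Under an any-advice reading they do not apply, and the dilution would be smaller.

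The main gain from the restriction is an interpretable measure of care for those to whom it applies; better power is secondary. The stated sample size is not itself in error, since its arithmetic reproduces. Imbalance between arms is a residual risk, mainly if follow-up levels are compared or advice rates move in both arms.

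**What to change.** In section 4.4 (endpoint 4) and the matching row of Table 9:

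- Report advice or referral for smoking cessation, diet and physical activity as three separate items.
- Define the smoking item as the percentage of consumers who smoke at the baseline survey, with the denominator fixed by the baseline answer and not the follow-up answer, so that the intervention cannot change who is counted.
- Keep all consumers as the denominator for diet and physical activity advice.
- Give the all-consumer smoking figure as descriptive only.

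The cost is wording. Smoking status is already among the AUSDRISK elements in the survey, so no new data are needed. The downside is that fewer consumers count for the smoking item; at every prevalence tested (30% to 80%) the larger difference more than makes up for this, but power for that item stays below 80% and should be reported as such.
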